### **GOALS:**

- **Main objective**

The measurement of pain intensity according to the NRS at different times: preoperative and at the 1st, 2nd, 12th and 24th postoperative hours.

- **Secondary objectives**

Postoperative opioid consumption and comparison of total cumulative consumption between the two groups.

It will also evaluated the degree of sensory and motor block, the easy of performance of the anesthetic technique, the degree of patient satisfaction and the record of short-term complications (first 24 hours post-intervention): hematoma, pruritus, nausea and/or vomiting.

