## PROTOCOL

All patients will be trained preoperatively in pain assessment using a Numerical Rating Scale (NRS) from 0 (absence of pain) to 10 (maximum pain endured). All patients will receive the same anesthesia and analgesia protocol; fentanyl, propofol and rocuronium prior to intubation.

Anesthetic maintenance with 1 MAC of sevoflurane and boluses of muscle relaxant and fentanyl if there is an increase >20% in blood pressure or above baseline heart rate. The anesthetic protocol will include analgesia with 1 g of paracetamol and 50 mg of dexketoprofen every 8 hours and a bolus of 0.1 mg/kg of intravenous dexamethasone. When the patient reports an NRS > 3 and functional impact, intravenous morphine will be administered at a dose of 0.04 mg/kg every 10 minutes until NRS < 3 in the PACU and tramadol 1 mg/kg in the ward. The nursing staff and the anesthesiologist in charge of the PACU will be blind to the block received by the patient in each study group.

Before general anesthesia, patients will be assigned to one of the study groups depending on the anesthesiologist responsible for performing the blocks.

**SHAC + SSN Group (anterior approach):** with the patient in the supine position and the arm placed in abduction and slight external rotation the ultrasound probe will be positioned in the transverse axis between the coracoid process and the humeral head. After identifying the tendon of the subscapularis muscle, a puncture will be performed in a lateral to medial plane and the local anesthetic will be deposited at two levels; one deep to the subscapularis tendon at the pericapsular level of the glenohumeral joint (5 ml of ropivacaine 0.2%), and another in withdrawal at about the level of the fascia that separates the subscapularis and deltoid muscles at a more superficial level (10 ml of 0.2% ropivacaine). Subsequently, the ultrasound probe will be positioned in the transverse axis at level with the neck to locate the suprascapular nerve through an anterior approach as it ran beneath the omohyoid muscle. After hydrodissecting the correct plane with saline solution 5 ml of 0.2% ropivacaine will be administered, depositing the local anesthetic under the lower belly of the omohyoid muscle.

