## **JUSTIFICATION OF SAMPLE SIZE**

Because no work of this nature has been carried out previously, a sample size calculation will be not performed and all patients who underwent surgery in the 12 months that the study data collection will last were consecutively included in the study.

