## **VARIABLES EVALUATED**

The main variable will be the measurement of pain intensity according to the NRS at different times: preoperative and at the 1st, 2nd, 12th and 24th postoperative hours. As secondary variables, postoperative opioid requirements will be assessed in the form of intravenous morphine, measured in mg (only during the 2 hours of the patient's stay in the Postanesthesia Care Unit), and tramadol (mg) up to 24 hours postoperatively.

The degree of sensory block will be also assessed by a cold sensitivity test with a cotton swab dipped in cold water applied to the skin of the upper third of the arm, which will be graded with a sensitive scale going from 0 to 2 (2 being normal sensitivity to cold, 1 hypoesthesia and 0 anesthesia). The degree of motor block upon arrival at the PACU will be assessed by the movement of the arm using a simple numerical scale (0 = cannot raise the extended arm  $> 45^\circ$  and 1 = can raise the extended arm  $> 45^\circ$ ), the ease of performance of the corresponding anesthetic technique by the anesthesiologist using a simple verbal scale (easy/medium difficulty/difficult), the appearance of adverse effects (postoperative nausea and/or vomiting, hematoma, pruritus, urinary retention), the degree of patient satisfaction (very satisfied, satisfied or dissatisfied) and the notification of complications related to the anesthetic techniques performed.

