## **STATISTICAL ANALYSIS PLAN**

Continuous quantitative variables will be expressed as mean and standard deviation and the results will be contrasted using the Student's T test if normality criteria will be met, failing which they will be expressed as median and range and contrasted using the Mann Whitney's U. The qualitative variables will be expressed in absolute numbers and relative frequencies and the results of both groups will be contrasted using the Chi square. In addition, Fisher's test will be applied when necessary. Normality tests will be conducted for all continuous quantitative variables. The Kruskal-Wallis technique will be also employed with post-hoc application of the Bonferroni test for the analyses. The data will be processed using SPSS software version 19.0 (IBM Corporation, Armonk, NY, USA), assuming a p-value below 0.05 as significant.

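### Patient satisfaction is recorded on a coarse, unbalanced three-option item at no stated time and compared by a test that ignores order, which may reduce sensitivity (minor, secondary variable)

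*Combined protocol and SAP*

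**What the plan says.** GOALS makes the degree of satisfaction a secondary objective: "the degree of patient satisfaction and the record of short-term complications (first 24 hours post-intervention". The 24-hour window in that sentence belongs to the complications, not to satisfaction.

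VARIABLES EVALUATED defines the item as "the degree of patient satisfaction (very satisfied, satisfied or dissatisfied". The same section fixes times for pain (preoperative and 1, 2, 12 and 24 h) and ties motor block to arrival in the PACU. It gives no time for satisfaction.

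STATISTICAL ANALYSIS PLAN says that for qualitative variables "the results of both groups will be contrasted using the Chi square", with Fisher's test when necessary, and a significance rule of "assuming a p-value below 0.05 as significant". JUSTIFICATION OF SAMPLE SIZE says "a sample size calculation will be not performed".

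**The concern.** The objective is a degree, but the item can grade only the favourable side. A neutral patient must pick a side, and mild and severe dissatisfaction are recorded alike. The planned test then treats the three options as unordered labels and discards part of what little grading there is.

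The open time of asking is a separate gap. An answer given in the PACU while the block is working and an answer at 24 h measure different things, and two hospitals could collect them differently.

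Satisfaction is the only overall judgement by the patient in the study. If answers cluster at the top, a finding of no difference would be hard to interpret.

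**Working it through.** **Is there a figure to reproduce?** No. The documents state no sample size, power, expected satisfaction distribution or allocation ratio ("patients will be assigned to one of the study groups depending on the anesthesiologist responsible for performing the blocks"). What follows is an illustration.

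**Inputs**
- From the documents: three options, chi-square, alpha 0.05.
- Assumed: two-sided test, 1:1 allocation, n = 40 per group, normally distributed latent satisfaction, and a shift of 0.5 SD between groups.
- Assumed reference distributions (very satisfied / satisfied / dissatisfied, %): 80/17/3, 70/25/5, 60/35/5 and 50/40/10.

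**Step 1: the comparison group.** Cut the latent normal at the reference cumulative proportions, then shift it. For 80/17/3 with an upward shift:
- Very satisfied: Φ(0.842 + 0.5) = 0.910.
- Dissatisfied: Φ(−1.881 − 0.5) = 0.009.
- Satisfied: the remaining 0.081.

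For 50/40/10 the same steps give 69.1/27.1/3.7%.

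**Step 2: planned chi-square (2 df, critical value 5.99).** The noncentrality is λ = n Σ (p − q)² / (p + q).
- 80/17/3: λ = 40 × (0.110²/1.710 + 0.089²/0.251 + 0.021²/0.039) ≈ 2.0, so power is about 23%. Direct simulation gives about 20%, because the dissatisfied cells are very sparse.
- 50/40/10: λ = 40 × (0.191²/1.191 + 0.129²/0.671 + 0.063²/0.137) ≈ 3.4, so power is about 36%.

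**Step 3: Mann-Whitney on the same three options.** The statistic is the midrank sum, with tie-corrected variance (n²/12)[(N + 1) − Σ(t³ − t)/(N(N − 1))], where N = 2n and t is the number of patients in each category. It was evaluated by simulation.

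**Step 4: Mann-Whitney on a 0-10 scale.** The assumed distribution spreads the favourable end: from 10 down to 0, 30, 20, 18, 12, 8, 5, 3, 2, 1, 0.5 and 0.5%. Similar top-heavy shapes give slightly lower figures.

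| n = 40 per group, 0.5 SD | Upward shift | Downward shift |
|---|---|---|
| Chi-square, three options | about 20-36% | about 30-40% |
| Mann-Whitney, three options | about 30-45% | about 40-50% |
| Mann-Whitney, 0-10 with favourable answers spread | about 50-53% | about 55% |

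**Step 5: what drives the gain?** Hold the top-category share equal across scales (upward shift, Mann-Whitney):
- 80% at the top: three levels 30%, five levels 28%, eleven levels 29%.
- 60% at the top: 41%, 41% and 41%.
- 50% at the top: three levels 44%, five levels 46-47%.

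Extra levels alone add about 0-3 points. The gain comes from using the order and from breaking up the top category.

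**Step 6: other sample sizes.** With 80, 60 or 40% very satisfied in the reference group and an upward shift, moving from chi-square to Mann-Whitney on three options gives:
- 50 per group: 28 to 36%, 39 to 49%, 46 to 56%.
- 100 per group: 51 to 62%, 69 to 78%, 77 to 86%.

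The ordered test is worth about 8 to 11 points in each case.

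**The case against.** A reader might infer that most answers will pile up at the top, that real differences between the blocks will be lost, and that a null result would be largely a product of the scale. The documents do not support this. They give no distribution of answers, and the item still separates very satisfied from satisfied, which is where any clustering would occur. With no sample size calculation, no power was promised for any endpoint. In the illustration a null result on 0-10 would also be weak evidence, at a little over 50% power.

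A second tempting reading is that the missing neutral option is what costs power. Step 5 shows otherwise: at an equal top share, a neutral option and a second dissatisfied grade add almost nothing. For the same reason a balanced five-level scale that keeps very satisfied as its top option is not a dependable remedy. A 0-10 scale helps only if patients spread over its upper end, which is itself an assumption. The size of the loss also depends on the direction of the shift and is smaller when the comparison group is less satisfied.

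It can also be said that the SAP mentions Kruskal-Wallis, which uses order and for two groups is equivalent to Mann-Whitney. But it ties that test to no variable, while its rule for qualitative variables is explicit.

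These points limit the claim to a possible loss of sensitivity. They do not answer the missing time of asking or the choice of an order-blind test.

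**Conclusion.** The concern holds as a minor improvement. The item is coarse and unbalanced, its timing is unstated, and the planned test ignores the order of its categories. Sensitivity may be reduced if many patients choose the top option. In the illustration with an upward shift, an ordered test on the same data recovers about 10 points, and a 0-10 scale that spreads the favourable answers adds roughly 5 to 20 more, depending on how strong the ceiling is.

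All of this rests on assumed values for N, allocation, shift, its direction and the response distributions. It does not show that differences will be missed. Satisfaction is one of several secondary variables, and "The main variable will be the measurement of pain intensity according to the NRS at different times" is untouched.

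**What to change.** - **VARIABLES EVALUATED:** record satisfaction once, at the 24 h pain assessment, on a 0-10 scale (0 = completely dissatisfied, 10 = completely satisfied).
- **STATISTICAL ANALYSIS PLAN:** name Mann-Whitney as the comparison for this variable and report the difference between groups with its 95% CI.
- **If the three-option item is kept, or data are already collected:** report the full distribution over all three categories by group, use an order-respecting test instead of chi-square, state when the question was asked, and note any ceiling as a limitation.

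The cost is one reworded item on the data form and one sentence in the analysis plan, with no extra contact because the 24 h assessment already exists. The downside is less direct comparability with any other use of the three-option item.

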## **STATISTICAL ANALYSIS PLAN**

Continuous quantitative variables will be expressed as mean and standard deviation and the results will be contrasted using the Student's T test if normality criteria will be met, failing which they will be expressed as median and range and contrasted using the Mann Whitney's U. The qualitative variables will be expressed in absolute numbers and relative frequencies and the results of both groups will be contrasted using the Chi square. In addition, Fisher's test will be applied when necessary. Normality tests will be conducted for all continuous quantitative variables. The Kruskal-Wallis technique will be also employed with post-hoc application of the Bonferroni test for the analyses. The data will be processed using SPSS software version 19.0 (IBM Corporation, Armonk, NY, USA), assuming a p-value below 0.05 as significant.

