## BACKGROUND AND JUSTIFICATION OF THE PROJECT

Arthroscopic shoulder surgery is related to a high incidence of postoperative pain, being rated as intense by 45% of patients in the immediate postoperative period (1). The management of these patients can be complex due to the high incidence of preoperative pain and its variability during the postoperative period, which is higher in patients undergoing rotator cuff repair surgery (2).

It is crucial to ensure adequate postoperative pain control in this type of intervention, especially in the context of major outpatient surgery. Adequate postoperative pain control can have several benefits, such as reducing hospital stay (3), accelerating postoperative rehabilitation (4), and improving long-term outcomes (5).

The PROSPECT guideline for rotator cuff repair surgery recommends associating a regional analgesic technique with a multimodal pharmacological approach to pain. (6).

Traditionally, the interscalene block has been considered the gold-standard for analgesia in shoulder surgery; However, its possible serious complications limit its use. Currently, most anesthesiologists choose to perform more distal peripheral nerve blocks of the brachial plexus (upper trunk block, supraclavicular block, infraclavicular block at the costoclavicular level, axillary nerve block...) which, although highly effective, continue to cause impairment. prolonged motor activity and are not free of complications (phrenic paralysis, transient nerve injuries, inadvertent vascular punctures...) (7).

Shoulder anterior capsular block (SHAC) has recently been described. It is a fascial block of the anterior capsule of the shoulder that aims to avoid motor impairment while maintaining optimal analgesic efficacy (8)(9). However, so far only anatomical and descriptive studies of small case series have been published. Therefore, this research work, with the objective of comparing the postoperative analgesic effectiveness of two regional analgesic techniques: the SHAC block associated with the suprascapular nerve block performed anteriorly vs. suprascapular and axillary nerve blocks performed posteriorly in operated patients. of the shoulder via arthroscopic procedures that cause intense postoperative pain.

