## **STUDY TYPE**

An observational study of paired cohorts, not randomized, is designed in two hospitals in northern Spain in the period between october 2023 and september 2024.

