## **RECRUITMENT AND RECRUITMENT OF PARTICIPANTS**

The anesthesiologist responsible for the operating room performed both the block of the anterior capsule of the shoulder and the suprascapular nerve via the anterior route and the blocks of the suprascapular and axillary nerves via the posterior route until the number of patients established in each of the groups is reached.

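### The main comparison is non-randomised, but the SAP tests it only with unadjusted two-group tests and makes no covariate use of the preoperative pain score it collects

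*Combined protocol and SAP*

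**What the plan says.** STUDY TYPE, repeated in the abstract, reads: "An observational study of paired cohorts, not randomized, is designed in two hospitals in northern Spain". No matching variable is given anywhere.

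VARIABLES EVALUATED defines the main variable as "pain intensity according to the NRS at different times: preoperative and at the 1st, 2nd, 12th and 24th postoperative hours". The preoperative score is thus listed beside the four postoperative scores as a time of the outcome.

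STATISTICAL ANALYSIS PLAN is one paragraph. For continuous variables, "the results will be contrasted using the Student's T test if normality criteria will be met". The fallback for data that are not normal is another unadjusted two-group test: "failing which they will be expressed as median and range and contrasted using the Mann Whitney's U". Categorical variables get chi-square or Fisher's test. It adds: "The Kruskal-Wallis technique will be also employed with post-hoc application of the Bonferroni test for the analyses". No covariate, hospital term or model is named.

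BACKGROUND gives a reason to care about baseline pain: "The management of these patients can be complex due to the high incidence of preoperative pain and its variability during the postoperative period".

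Two sections describe how groups form. PROTOCOL says "patients will be assigned to one of the study groups depending on the anesthesiologist responsible for performing the blocks". RECRUITMENT says "The anesthesiologist responsible for the operating room performed both the block of the anterior capsule of the shoulder" and continues that the same person also did the posterior blocks, until a set number per group is reached.

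**The concern.** Without randomisation, nothing in the design makes the two groups alike in preoperative pain or in hospital. The analysis is then the main remaining place to deal with such differences, and the tests listed cannot do so. Moving from Student's t to Mann-Whitney when data are skewed changes the distributional assumption, not the comparability of the groups.

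The aim is to compare the analgesic effectiveness of two techniques. If patients in one group start with more pain, or come mainly from one hospital, part of the crude difference in postoperative NRS would reflect that and not the block. More patients would make the crude estimate more precise without moving it closer to the block effect. Choosing covariates after the data are seen would be open to the charge of selection, so the adjustment has to be written down beforehand.

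**Working it through.** There is no planned figure to reproduce. JUSTIFICATION OF SAMPLE SIZE states that no calculation is made, and no SD, effect size or correlation appears anywhere.

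**Textual check**

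- Allocation: not randomised, two hospitals (STUDY TYPE).
- Tests: Student's t, Mann-Whitney, chi-square, Fisher and Kruskal-Wallis with Bonferroni. All are for independent groups and none takes a covariate.
- Other control of confounding: none. The word *paired* has no matching variable behind it and no paired test; inclusion is consecutive.
- Preoperative NRS: collected and, as a continuous variable, contrasted between groups. An imbalance would be seen. Nothing uses it to adjust the postoperative comparison.
- Operator: under PROTOCOL, technique follows the anaesthesiologist, so operator and block may coincide. RECRUITMENT can be read as one anaesthesiologist doing both techniques, with no rule for who receives which. Neither reading balances the groups, but operator confounding follows only from the first.
- Procedure: the abstract restricts the population to rotator cuff repair; section 1.1 admits any shoulder arthroscopy. Procedure mix matters only under the second.

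**Illustration (all inputs assumed)**

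Take n = 50 per group, SD 2.5 before and after surgery, pre/post correlation r = 0.3 to 0.5, no true block effect and a systematic preoperative difference d.

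- SE of the crude difference = SD × √(2/n) = 2.5 × √(2/50) = 0.5.
- Carried-over difference b = r × d. For d = 1, b is 0.3 to 0.5 point.
- False positives = P(|Z + b/SE| > 1.96). For d = 1, b/SE is 0.6 to 1.0, giving 9.2% to 17.0%. For d = 0.5, b/SE is 0.3 to 0.5, giving 6.0% to 7.9%.
- Over n = 30 to 100 and SD 2 to 3, the ranges are 6.7% to 42.4% for d = 1 and 5.4% to 14.3% for d = 0.5.
- A simulated skewed score, rounded and limited to 0–10 (n = 50, d = 1), gave 8.5% to 15.9% for the t test, 8.5% to 15.6% for Mann-Whitney and about 5% for ANCOVA. The ANCOVA result is nearly built in, because measured preoperative NRS was the only source of imbalance.

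**What adjustment does to precision**

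- With no operator term, the 95% half-width is multiplied by √(1 − r²) = 0.954 to 0.866, so 1.96 × 0.5 = 0.98 becomes 0.935 to 0.849.
- With k operators per arm, each using one technique, and m = n/k patients each, one form of the half-width is t(2k−2) × SE × √(1 − r²) × √(1 + (m − 1) × ICC). The other puts the ICC on total variance: t(2k−2) × SD × √(2 × (ICC/k + (1 − ICC)(1 − r²)/n)). Example for the first form, k = 3, r = 0.5, ICC 0.02: 2.78 × 0.5 × 0.866 × √(1 + 15.67 × 0.02) ≈ 1.38.
- Ratio to the crude interval across both forms, for ICC 0.02 to 0.05, r = 0.3 to 0.5 and n = 30 to 100: 2.2 to 4.0 with 2 operators per arm, 1.3 to 2.3 with 3, 1.07 to 1.61 with 5, 0.97 to 1.34 with 8.

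**Residual confounding**

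A single NRS reading has error. If its reliability is 0.7 to 0.9 (assumed), a 1-point true-score difference leaves r/reliability − r after adjustment: from 0.3/0.9 − 0.3 = 0.03 to 0.5/0.7 − 0.5 = 0.21 point.

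**The case against.** The strongest reply is that nothing in the documents ties technique to preoperative pain or to hospital. The allocation rule that PROTOCOL states is the responsible anaesthesiologist, who need not choose by pain. The common anaesthetic protocol, the blinded PACU staff and consecutive inclusion remove some biases. Preoperative NRS would be compared between groups, so an imbalance would be visible. If each operator uses one technique, the best-documented threat is operator, and covariates cannot cleanly remove it.

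Much of this stands. A reader might infer that the groups will differ at baseline, or that an imbalance would pass unnoticed as a block effect; the documents support neither. A reader might also take the false-positive percentages as a property of this study. They depend on a systematic 1-point difference that no section supports, and at half a point the effect is small. Nor is an interval allowing for operator always wider than the crude one: that holds with 2 or 3 operators per arm, but at 8 it can be slightly narrower, and the number of operators is not given.

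What the reply does not remove is the gap itself. Blinding and a common protocol do not balance who receives which block, and seeing an imbalance is not adjusting for it.

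**Conclusion.** The concern holds as a design argument. The comparison is non-randomised, every test listed is unadjusted, and the one baseline measure most closely related to the outcome is collected without a stated covariate role. The main between-group difference is therefore open to confounding by baseline pain and, if technique use differs by site, by hospital. This should be corrected before analysis, because it concerns the main variable and the key covariate is already in hand.

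Its size in this study is unknown; the figures above show the mechanism and do not set the importance of the point. Confounding by operator or by procedure is conditional on how the conflicting sections are reconciled. It also cannot be concluded that hospital, operator or procedure type go unrecorded: VARIABLES EVALUATED does not list them, but the data form is not shown.

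**What to change.** Define the main outcome as NRS at 1, 2, 12 and 24 h and treat preoperative NRS as a baseline covariate. Replace the crude test of the main variable with a prespecified ANCOVA at each time, or a mixed model with group, time and group-by-time. Adjust for preoperative NRS, and for hospital if both techniques are used at both sites. Report adjusted differences with 95% confidence intervals. Because NRS is bounded and may be skewed, add a sensitivity analysis with robust standard errors or ordinal regression, using the same covariates.

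Secondary reconciliations:

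- Confirm that hospital and operator are recorded.
- Reconcile PROTOCOL with RECRUITMENT. If operators use both techniques, add operator as a factor. If each uses only one, state that block and operator effects cannot be cleanly separated and limit the conclusion; with one operator per arm no analysis can separate them.
- Reconcile the population in the abstract with section 1.1. Add procedure type as a covariate, and confirm it is recorded, only if section 1.1 governs.
- Delete *paired*, or name the matching variables and use a paired analysis.

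The cost is one model and one sensitivity analysis, a few degrees of freedom, and an amendment sent for re-evaluation as ETHICAL-LEGAL ASPECTS requires. Adjustment covers measured confounders only, the main model assumes a linear relation with preoperative NRS, and error in a single NRS reading can leave some baseline confounding. With few operators per arm, an interval that allows for operator will be wider than the crude one.

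### The plan names Student's t test with no provision for unequal variances, although the protocol does not secure equal groups; naming Welch's test is a small, nearly free improvement

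*Combined protocol and SAP*

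**What the plan says.** The Statistical Analysis Plan gives one rule for continuous variables. They are summarised by mean and SD, and the choice of test turns on normality alone: "the results will be contrasted using the Student's T test if normality criteria will be met". Where a variable does not pass, the plan switches both the summary and the test: "failing which they will be expressed as median and range and contrasted using the Mann Whitney's U". Each variable is checked separately: "Normality tests will be conducted for all continuous quantitative variables". Significance is declared "assuming a p-value below 0.05 as significant", with sidedness not stated. The section does not mention equal variances, a variance check, an unequal-variance version of the t test, or a confidence interval.

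On group sizes the protocol points two ways.

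- **Sizes left open.** Under Protocol, "patients will be assigned to one of the study groups depending on the anesthesiologist responsible for performing the blocks". Under Justification of Sample Size, no calculation is made and "all patients who underwent surgery in the 12 months that the study data collection will last were consecutively included in the study".
- **Sizes preset or matched.** Under Recruitment, blocks are performed "until the number of patients established in each of the groups is reached". Study Type describes "An observational study of paired cohorts, not randomized".

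No section gives a number per group, an allocation ratio, a pairing or matching rule, or an SD.

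**The concern.** Student's t test, taken by its name, pools the two sample variances. Normality is only one of its assumptions; the other is equal variance. When the groups are of similar size, unequal variance hardly matters. When they are not, the pooled standard error is weighted towards the variance of the larger group. If the smaller group is the more variable, the standard error is too small and the test rejects too often. If the larger group is the more variable, the standard error is too large and power is lost. An interval built on the pooled standard error is wrong in the same direction.

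Both conditions are possible here. Group sizes that depend on who performs the blocks, at two hospitals over a fixed period, may well differ. Spread may differ too: on a scale bounded at 0, a group with lower pain can have its scores compressed. The documents neither show nor exclude this.

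**Working it through.** **Inputs.** From the Statistical Analysis Plan: Student's t test and a 0.05 threshold. Two-sided testing is assumed. The documents give no group sizes or SDs, so size ratios from 1:1 to 4:1 and SD ratios from 1 to 2 are assumed. The plan states no power or sample size figure that could be reproduced.

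**Formula.** Let r be the size ratio (group 1 to group 2) and s the SD ratio (group 1 to group 2), with the variance of group 2 set to 1. In large samples, up to a common factor:

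- variance of the mean difference that the pooled test assumes: E = [(r·s² + 1)/(r + 1)] × (1/r + 1)
- true variance: T = s²/r + 1
- true two-sided error: 2 × [1 − Φ(1.96 × √(E/T))]

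**Equal groups, r = 1.** E = s² + 1 = T, so the error is 5.0% whatever the SD ratio. Simulation at 40 v 40 with SDs 2.5 and 1.5 gave 4.9% for both tests.

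**Mild imbalance, 1.5:1, SD ratio 1.5.**
- Larger group more variable (s² = 2.25): E = 1.75 × 1.667 = 2.917, T = 2.5, √(E/T) = 1.080, error 3.4%.
- Smaller group more variable (s² = 0.444): E = 0.667 × 1.667 = 1.111, T = 1.296, √(E/T) = 0.926, error 7.0%.

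**Strong imbalance, 3:1, SDs 2.5 and 1.5 (ratio 1.67).**
- Larger group more variable (s² = 2.778): E = 3.111, T = 1.926, √(E/T) = 1.271, error 1.3%.
- Smaller group more variable (s² = 0.36): E = 0.693, T = 1.12, √(E/T) = 0.787, error 12.3%.

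Simulation of normal data (40,000 replicates, equal means):

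| Sizes, SDs | Pooled t | Welch |
|---|---|---|
| 20 v 60, smaller group 2.5, larger 1.5 | 12.7% | 5.1% |
| 20 v 60, smaller group 1.5, larger 2.5 | 1.3% | 4.9% |
| 30 v 60, smaller group 2.5, larger 1.5 | 9.3% | 4.8% |
| 30 v 60, smaller group 1.5, larger 2.5 | 2.3% | 5.0% |
| 20 v 60, smaller group 2.5, larger 2.0 | 7.9% | 5.0% |
| 20 v 60, smaller group 2.0, larger 2.5 | 2.8% | 4.9% |

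These are scenarios, not bounds: at 4:1 with SD ratio 2 the formula gives 0.4% or 17.9%.

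**How often the t test would be used for NRS.** The plan names no normality test, so Shapiro-Wilk with p > 0.05 in both groups was assumed. NRS was generated as a normal value rounded and clipped to 0-10, with SDs 2.5 and 1.5, sizes 20 v 60 and 30 v 60, and underlying means from 1.5 to 5. With the smaller group more variable, the t test was reached in 0% to 8% of runs. In the other direction it was reached in up to about half of the runs, and only at mid-scale means. In the over-rejecting direction Mann-Whitney itself rejected in about 7% to 9% of runs. On unclipped normal data at 20 v 60 it rejected 8.5%, or 2.6% with the SDs reversed.

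**Cost of Welch when variances are equal** (assumed SD 2, difference 1.3), power of pooled v Welch: 40 v 40, 82.0% v 82.0%; 30 v 60, 82.2% v 81.7%; 20 v 60, 70.1% v 68.4%.

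**The case against.** The case against has four parts.

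1. **The figures rest on ratios the documents do not give.** This stands. A reader might infer that the study's 5% error rate lies anywhere between about 1% and 13%. That span comes from one assumed configuration, about 3:1 with an SD ratio near 1.7. Milder ratios give much less and stronger ones give more.

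2. **Group sizes may be preset.** A reader might infer that sizes are simply left to who is on duty. The Recruitment section and the design label point the other way, and with equal groups the problem disappears. This stands as a limit on the claim. It does not remove the point, because no number or pairing rule appears, an established number per group need not be the same number in both, and consecutive inclusion of everyone over 12 months conflicts with it.

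3. **The t test may rarely be used for NRS.** This is the strongest objection, and it stands. Under the assumptions above, the over-rejecting scenario hardly ever reaches the t test, so swapping Student for Welch alone would seldom change the primary result. It does not follow that the plan is safe, since Mann-Whitney is also affected by unequal spread. The rule also covers every continuous variable, including opioid amounts, and should be valid whenever it is used.

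4. **The pooled form is inferred from the name.** True: the text neither states nor excludes an unequal-variance version. The same edit settles it.

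**Conclusion.** The point holds in a limited form. The plan makes normality the only condition for Student's t test, and the protocol does not secure the equal group sizes that would make unequal variances harmless. If the t test is used and both size and spread differ, the pooled test loses its 5% level. Under assumed ratios the error is about 3.4% or 7.0% at 1.5:1 with SD ratio 1.5, and about 1.3% or 12% to 13% at 3:1 with SD ratio 1.67, against about 5% for Welch. With equal groups the error is about 5% with either test.

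The documents do not show that the groups will be unequal, that the spreads will differ, or that the primary NRS comparison will use the t test. This is therefore a minor improvement and not evidence that the planned analysis is invalid. It also leaves the larger weakness of the design untouched: Welch's test does nothing about confounding when the block depends on the anesthesiologist.

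**What to change.** In the Statistical Analysis Plan, replace Student's t test by Welch's unequal-variance t test for all comparisons of means. Report the mean difference with its 95% confidence interval, and do no preliminary test of variances.

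For NRS, state that the mean difference by Welch is reported at each time point whatever the normality test shows. Without this sentence the change would rarely touch the primary variable.

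Separately, reconcile Study Type, Protocol, Recruitment and Justification of Sample Size on whether group sizes are preset, matched or left open. If they are preset, give the numbers.

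The cost is a phrase and a sentence. If variances are in fact equal, power falls by nothing at 40 v 40, by about 0.5 points at 30 v 60 (82.2% − 81.7%) and by about 1.7 points at 20 v 60 (70.1% − 68.4%), under the assumptions shown. No extra data are needed.
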